# **5.4.** End of Study Definition

**Primary Completion:** The primary completion date is defined as the date when the last subject is assessed or receives an intervention for the final collection of data used for the primary endpoint, whether the study concluded as planned or was terminated early. The planned primary completion date for this study is the date when the last subject has completed the assessments for Week 4. If the study is terminated early, then the primary completion date will be the date of the last visit for the last subject in the study.

**End of Study:** The end of study is defined as the date of the last visit of the last subject or last scheduled procedure shown in the schedule of assessments for the last subject in the study globally.

## 6. STUDY OBJECTIVES

# 6.1. Primary

The primary objective of this study is:

• To evaluate the efficacy of crinecerfont, compared with placebo, in reducing adrenal steroid levels during a glucocorticoid-stable period.

# 6.2. Secondary

The secondary objectives of this study are the following:

- To evaluate the efficacy of crinecerfont, compared with placebo, in reducing daily glucocorticoid dosage while maintaining adrenal androgen control.
- To evaluate the effect of crinecerfont, compared with placebo, on clinical endpoints associated with supraphysiologic glucocorticoid dosing and androgen excess.
- To evaluate plasma concentrations of crinecerfont and metabolites.
- To assess the safety and tolerability of crinecerfont.

## 7. STUDY DESIGN

This is a Phase 3, randomized, double-blind, placebo-controlled study to evaluate the efficacy, safety, and tolerability of crinecerfont versus placebo administered bid with breakfast and evening meals for 28 weeks in approximately 81 pediatric subjects with classic CAH due to 21-hydroxylase deficiency. Eligible subjects will be randomly assigned in a 2:1 ratio (active:placebo) to either crinecerfont (25 mg bid via oral solution for subjects 10 to <20 kg, 50 mg bid via oral solution for subjects 20 to <55 kg, or 100 mg bid via oral capsules for subjects ≥55 kg) or matching placebo (oral solution placebo for subjects <55 kg and oral capsule placebo for subjects ≥55 kg). Dose assignment from Day 1 to Week 28 will be based on the subject's weight at Day 1. After the 28-week placebo-controlled treatment period, there will be a 24-week, open-label treatment period, during which all subjects will receive crinecerfont at doses based on their Week 28 body weight.

At Month 12 (Week 52), subjects will have the option to participate in an OLE (Section 9.11.2). During the OLE, subjects will continue to receive crinecerfont at their weight-based dose, unless the subject has inadequate efficacy (in the opinion of the investigator), in which case their crinecerfont dose can be increased by doubling the evening dose. At Month 12, subjects can also elect to switch the crinecerfont formulation (oral solution or capsule) based on preference. Further guidance on changes to crinecerfont dosing in the OLE is provided in Appendix B. Subjects have the option to remain in the OLE until crinecerfont becomes commercially available, the Sponsor elects to discontinue development of crinecerfont for CAH, or the Sponsor elects to discontinue the study.

# 7.1. Screening Period (Weeks -4 up to Day -1)

Prior to any study-related procedures, written informed consent from subject's parent(s) or legal guardian(s) with signed and witnessed study subject assent will be obtained (which may be done remotely, if allowed and remote consenting procedures are in place), as required by the governing IRB or ethics committee and according to local laws and regulations. Subjects will undergo screening for up to 4 weeks (Week -4 to Day -1) to determine eligibility. The screening period can be extended by up to 4 weeks after discussion with and approval of the Medical Monitor to allow for delayed screening laboratory results that are needed to determine eligibility or to accommodate other extenuating logistical issues, such as scheduling. Prior to the blood sample collection during screening, subjects will be asked to take their evening glucocorticoid dose the night before prior to 2100 hours and hold their morning dose of glucocorticoid and fludrocortisone (if applicable), but do not need to be fasting. Rescreening is permitted if a subject does not meet all eligibility requirements and returns to be rescreened. A subject that has failed screening twice may not be rescreened again without prior permission from the Medical Monitor.

# 7.2. Randomized, Double-Blind, Placebo-Controlled Treatment Period (Day 1 up to Week 28)

For visits at which blood samples are collected, subjects should take their evening glucocorticoid dose (if applicable) the night before prior to 2100 hours and hold their morning dose of glucocorticoid, fludrocortisone (if applicable), and study drug (after Day 1) until after predose blood sample collection, with dosing to occur between approximately 0800 and 0830 hours with breakfast. For blood tests obtained at the study site, subjects should bring their morning dose of

glucocorticoid, fludrocortisone (if applicable), and study drug (after Day 1) with them to the study site to take at the study site (with dosing to occur between approximately 0800 and 0830 hours with breakfast). Except for the screening visit, subjects should be fasting after midnight the night before until after the predose blood sample collection(s) but should be encouraged to drink water to avoid any hypovolemic status. Subjects <6 years of age for whom the investigator deems that fasting until 0800 hours is not feasible can have a snack(s) if needed but should wait to have breakfast with morning dosing.

#### Glucocorticoid-Stable Period

On Day 1, subjects who are >6 years of age with a body weight >20 kg should arrive at the study site for the serial blood sampling procedure and dosing, with dosing to occur between approximately 0800 and 0830 hours. Blood samples will be obtained serially over approximately 6 hours, with 2 baseline samples obtained approximately 15 minutes before the morning glucocorticoid dose and again immediately prior to the morning glucocorticoid dose administration (with dosing to occur between approximately 0800 and 0830) and at 2, 3, 4, and 6 hours after the morning glucocorticoid dose, for a total of 6 blood sampling time points. Subjects who are <6 years of age or with a body weight <20 kg will have a blood sample collection prior to their morning glucocorticoid dose only (with dosing to occur between approximately 0800 and 0830 hours). For all subjects, salivary samples for adrenal androgens and precursors will be collected in the early morning (0600 hours), at approximately 0800 hours prior to the morning glucocorticoid dose, at approximately 3 and 6 hours after the morning glucocorticoid dose, and in the evening (within 30 minutes prior to the evening dose of glucocorticoid; if subject is not on an evening glucocorticoid dose, then prior to bedtime). The salivary samples at approximately 0800 hours prior to dosing and 3 and 6 hours after dosing should be collected at approximately the same time as any corresponding blood samples (as applicable). Any midday glucocorticoid dose that the subject is receiving should be taken after the 6-hour postdose blood and salivary samples are collected. During the study, the exact timing of the blood and saliva samples, and the morning glucocorticoid, mineralocorticoid, and/or study drug dose (and breakfast), may be adjusted by  $\pm 1$  hour to accommodate site and subject schedules if needed as long as this is done consistently per subject and the relative times between the sample(s) and the dose(s) are maintained.

Subjects will be randomized on Day 1 in a 2:1 ratio (active:placebo). Randomization will be stratified by pubertal stage (Tanner breast or genital stage 1 or 2 versus 3, 4, or 5) and sex. From the evening of the Day 1 visit (after all Day 1 assessments have been performed) until the morning of the Week 28 visit, all subjects will receive blinded study drug based on their Day 1 weight (25 mg bid via oral solution for subjects 10 to <20 kg, 50 mg bid via oral solution for subjects 20 to <55 kg, or 100 mg bid via oral capsules for subjects ≥55 kg). Study drug will be administered bid with the subject's breakfast and evening meals (each dose separated by approximately 12 hours).

From Day 1 until Week 4, subjects should maintain a stable glucocorticoid regimen to the extent possible, except for stress dosing if needed for illness or other significant physical stress, in order to assess the direct effect of study drug on adrenal androgens and precursors. Stress dosing of glucocorticoid (at any time during the study) can be based on guidance provided by the investigator, the subject's treating physician, or guidelines provided in the protocol (Appendix A).

# Glucocorticoid-Adjustment Period

At the Week 4 visit, subjects  $\geq 6$  years of age with a body weight  $\geq 20$  kg should arrive at the study site for the serial blood sampling procedure and dosing, with dosing to occur between approximately 0800 and 0830 hours with breakfast. Blood samples will be obtained serially over approximately 6 hours, with 2 baseline samples (obtained approximately 15 minutes before and again immediately prior to the morning glucocorticoid and study drug dose, with dosing to occur between approximately 0800 and 0830 hours with breakfast). Blood samples will also be obtained at 2, 3, 4, and 6 hours after dosing. PK blood samples will be obtained at the same time points with the exception of only 1 required predose sample. Subjects who are <6 years of age or with a body weight <20 kg will have blood sample collection prior to the morning glucocorticoid and study drug dose only (with dosing to occur between approximately 0800 and 0830 hours with breakfast). For all subjects, salivary samples for adrenal androgens and precursors will be collected in the early morning (0600 hours), at approximately 0800 hours prior to the morning glucocorticoid and study drug dose, at approximately 3 and 6 hours after the morning glucocorticoid and study drug dose, and in the evening (within 30 minutes prior to the evening dose of glucocorticoid; if subject is not on an evening glucocorticoid dose, then prior to bedtime). The salivary samples at approximately 0800 hours prior to dosing and 3 and 6 hours after dosing should be collected at approximately the same time as any corresponding blood samples (as applicable). Any midday glucocorticoid dose that the subject is receiving should be taken after the 6-hour postdose blood and salivary samples are collected. During the study, the exact timing of the blood and saliva samples, and the morning glucocorticoid, mineralocorticoid, and/or study drug dose, may be adjusted by  $\pm 1$  hour to accommodate site and subject schedules if needed, as long as the relative times between the sample(s) and the dose(s) are maintained.

From Week 4 until Week 28, the subject's glucocorticoid dose should be adjusted according to their A4 levels, with the goal to reach a target dose of 8 to 10 mg/m²/day (in hydrocortisone dose equivalents adjusted for body surface area [BSA]) at Week 28, while A4 is controlled, ie, ≤120% of the baseline value or ≤ upper limit of normal (ULN), according to sex and either age (for Tanner stage 1) or pubertal stage (for Tanner stages 2 to 5). The calculation of glucocorticoid dose in hydrocortisone equivalents adjusted for BSA at Day 1 and Week 28 will be based on height and weight measurement at Day 1 and Week 28, respectively. BSA will be updated at Week 16 if height measurement is obtained at Week 16.

Glucocorticoid dose adjustments can occur in as few as 1 or up to 4 steps, depending on the starting and target glucocorticoid doses and the amount of dose adjustment at each step. Reductions in the glucocorticoid dose should follow the guideline of first reducing the most nonphysiologic glucocorticoid type and timing. The target glucocorticoid dose should be within the range of 8 to 10 mg/m²/day while A4 levels are controlled and as long as there is no evidence of glucocorticoid insufficiency. The dose could be lower than this range if the investigator considers this appropriate depending on practical issues considered in clinical practice related to available dosage strengths but will not be mandated to be lower than this range. Before any glucocorticoid dose reduction is implemented, the investigator will evaluate the subject for any symptoms suggestive of glucocorticoid insufficiency using a standardized checklist and will arrange for follow-up if needed after the dose reduction.

The first glucocorticoid dose adjustment step at approximately Week 6 (or when the Week 4 lab results are available) should be guided by the change in A4 at Week 4 from baseline. A

suggested guideline is provided in Table 3, but the exact amount adjusted may differ from this guideline based on practical issues considered in clinical practice related to available dosage strengths. The investigator should contact the subject/guardian once the Week 4 lab results are available in order to provide guidance on the amount of the first glucocorticoid dose adjustment.

Table 3: Guide for Glucocorticoid Dose Adjustments During the Randomized, Placebo-Controlled Treatment Period

Percent Change From Baseline in Serum Androstenedione	Androstenedione Level	Glucocorticoid Dose Adjustment
Any increase	>ULN	Consider whether glucocorticoid dose needs to be increased
Any increase	≤ULN	Maintain current glucocorticoid dose
No change a	Any	Maintain current glucocorticoid dose
Decrease of ≤20%	Any	1 to 2 mg/m²/day glucocorticoid dose decrease
Decrease of >20% to ≤40%	Any	2 to 3 mg/m²/day glucocorticoid dose decrease
Decrease of >40%	Any	3 to 4 mg/m  /day glucocorticoid dose decrease

ULN=upper limit of normal.

A follow-up blood test (with salivary sample collection) should be arranged approximately 2 weeks later at Week 8 (at home or the study site).

If needed, subsequent glucocorticoid dose adjustment steps should occur when lab results are available (at approximately Week 10, Week 14, and Week 18) with follow-up blood and salivary tests at Week 12 (at home or the study site, if the glucocorticoid dose was previously modified), Week 16 (at home or the study site), and Week 20 (at home or the study site, if the glucocorticoid dose was previously modified) (Table 4). The target amount of glucocorticoid dose reduction at each step is approximately 1 to 4 mg/m²/day but should be guided by the A4 level at the preceding blood test as well as on practical issues considered in clinical practice related to available dosage strengths.

Table 4: Schedule for Blood Tests and Potential Glucocorticoid Dose Adjustments
During the Randomized, Placebo-Controlled Treatment Period

Blood Test (Including Androstenedione)	Glucocorticoid Dose Adjustment Step
Week 8 (at home or the study site)	Potential GC dose adjustment (if needed) at approximately Week 10 (or when Week 8 labs available)
Week 12 (at home or the study site)	Potential GC dose adjustment (if needed) at approximately Week 14 (or when Week 12 labs available)
Week 16 (at home or the study site)	Potential GC dose adjustment (if needed) at approximately Week 18 (or when Week 16 labs available)
Week 20 (at home or the study site)	Potential GC dose increase (if needed) at approximately Week 22 (or when Week 20 labs available) to maintain androstenedione control

GC=glucocorticoid

<sup>a Within reasonable variability in the opinion of the investigator.

At all visits, if A4 is >120% of baseline and >ULN, increase glucocorticoid dose as appropriate in order to maintain A4 control.

For the Week 28 visit, subjects should hold their morning glucocorticoid and study drug dose until after the predose blood samples are collected, with dosing to occur between approximately 0800 and 0830 hours with breakfast. For subjects  $\geq 6$  years of age with a body weight  $\geq 20$  kg, another blood sample will be collected approximately 3 hours after the morning glucocorticoid and study drug dose. For all subjects, salivary samples will be collected over the course of the day: at approximately 0600 hours, at approximately 0800 hours prior to morning glucocorticoid and study drug dosing and 3 and 6 hours after dosing, and within 30 minutes prior to the evening dose of glucocorticoid (if subject is not taking evening glucocorticoid dose, then prior to bedtime). Any midday glucocorticoid dose that the subject is receiving should be taken after the 6-hour postdose salivary sample is collected.

# 7.3. Open-Label Treatment Period (Week 28 to Week 52)

From the evening of the Week 28 visit (after all Week 28 assessments have been performed) until the morning of the Week 52 visit, all subjects will receive active study drug based on their Week 28 weight (crinecerfont; 25 mg bid via oral solution for subjects 10 to <20 kg, 50 mg bid via oral solution for subjects 20 to <55 kg, or 100 mg bid via oral capsules for subjects ≥55 kg) with breakfast and evening meals. Subjects and investigators will remain blinded to subjects' randomized treatment group assignment during the entire study. From Week 28 until Week 32, subjects should maintain a stable glucocorticoid regimen to the extent possible, except for stress dosing if needed for illness or other significant physical stress. A blood sample will be collected at Week 32 (at home or the study site).

For subjects who are on >11 mg/m²/day glucocorticoid dose (in hydrocortisone dose equivalents adjusted for BSA [based on weight and height at Week 28]) at Week 32, further adjustments in glucocorticoid dose should be made following guidelines similar to that used during the placebo-controlled period with the goal to reach a target dose of 8 to 10 mg/m²/day in hydrocortisone dose equivalents adjusted for BSA at Week 52, while A4 is controlled. The calculation of glucocorticoid dose in hydrocortisone equivalents adjusted for BSA at Week 52 will be based on height and weight measurement at Week 52. BSA will be updated at Week 40 if height measurement is obtained at Week 40.

The first glucocorticoid dose adjustment step during this period (if done) should be guided by the serum A4 change at Week 32 (compared with Week 28), after the subject has been on open-label active study drug as well as stable glucocorticoid regimen (to the extent possible) for 4 weeks. A suggested guideline is provided in Table 5 but the exact amount adjusted may differ from this guideline based on practical issues considered in clinical practice related to available dosage strengths. The investigator should contact the subject/guardian once the Week 32 lab results are available in order to provide guidance on the amount of the first glucocorticoid dose adjustment (if needed) during the open-label treatment period.

Table 5: Guide for Glucocorticoid Dose Adjustment During the Open-Label Treatment Period

Percent Change from Week 28 in Serum Androstenedione	Androstenedione Level	Glucocorticoid Dose Adjustment
Any increase	>ULN	Consider whether glucocorticoid dose needs to be increased
Any increase	≤ULN	Maintain current glucocorticoid dose
No change a	Any	Maintain current glucocorticoid dose
Decrease of ≤20%	Any	1 to 2 mg/m²/day glucocorticoid dose reduction
Decrease of >20% to ≤40%	Any	2 to 3 mg/m²/day glucocorticoid dose reduction
Decrease of >40%	Any	3 to 4 mg/m²/day glucocorticoid dose reduction

ULN =upper limit of normal

If the glucocorticoid dose is modified at approximately Week 34, a follow-up blood test (with salivary sample collection) should be arranged approximately 2 weeks later at Week 36 (at home or the study site).

If needed, subsequent glucocorticoid dose adjustments should occur at approximately Week 38 and Week 42 (or when lab results are available) with follow-up blood and salivary tests at Week 40 (at home or the study site) and Week 44 (at home or the study site, if the glucocorticoid dose was previously modified during the open-label treatment period) (Table 6). The target amount of glucocorticoid dose reduction at each step is approximately 1 to 4 mg/m²/day but should be guided by the A4 level at the preceding blood test as well as practical issues considered in clinical practice related to available dosage strengths.

Table 6: Schedule for Blood Tests and Potential Glucocorticoid Dose Adjustments
During the Open-Label Treatment Period

Blood Test (Including Androstenedione)	Glucocorticoid Dose Adjustment Step
Week 36 (at home or the study site)	Potential GC dose adjustment (if needed) at approximately Week 38 (or when Week 36 androstenedione result is available)
Week 40 (at home or the study site)	Potential GC dose adjustment (if needed) at approximately Week 42 (or when Week 40 androstenedione result is available)
Week 44 (at home or the study site)	Potential GC dose increase (if needed) at approximately Week 46 (or when Week 44 labs available) to maintain androstenedione control

GC=glucocorticoid; ULN=upper limit of normal

At all visits, if A4 is >120% of baseline and >ULN, increase glucocorticoid dose as appropriate in order to maintain A4 control.

<sup>a Within reasonable variability in the opinion of the investigator.

For the Week 52 visit, subjects should hold their morning glucocorticoid and study drug dose until after the predose blood samples are collected, with dosing to occur between approximately 0800 and 0830 hours with breakfast. For subjects ≥6 years of age with a body weight ≥20 kg, another blood sample will be collected approximately 3 hours after the morning glucocorticoid and study drug dose. For all subjects, salivary samples will be collected over the course of the day: at approximately 0600 hours, at approximately 0800 hours prior to morning glucocorticoid and study drug dosing and 3 and 6 hours after dosing, and within 30 minutes prior to the evening dose of glucocorticoid (if subject is not taking evening glucocorticoid dose, then prior to bedtime). Any midday glucocorticoid dose that the subject is receiving should be taken after the 6-hour postdose salivary sample is collected.

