## 9.3.2.2. Glucocorticoid Dose Adjustment During Open-Label Treatment Period

From Week 28 until Week 32, subjects should maintain a stable glucocorticoid regimen to the extent possible, except for stress dosing if needed for illness or other significant physical stress. A blood sample will be collected at Week 32 (at home or the study site).

For subjects who are on >11 mg/m²/day glucocorticoid dose at Week 32, further adjustments in glucocorticoid dose should be made following guidelines similar to that used during the placebocontrolled period, with the goal to reach a target dose of 8 to 10 mg/m²/day in hydrocortisone dose equivalents adjusted for BSA at Week 52, while A4 is controlled. The calculation of glucocorticoid dose in hydrocortisone equivalents adjusted for BSA at Week 52 will be based on height and weight measurement at Week 52. BSA will be updated at Week 40 if height measurement is obtained at Week 40.

The first glucocorticoid dose adjustment step during this period (if done) should be guided by the serum A4 change at Week 32 (compared with Week 28), after the subject has been on open-label active study drug as well as stable glucocorticoid regimen (to the extent possible) for 4 weeks. A suggested guideline is provided in Table 11 but the exact amount adjusted may differ from this guideline based on practical issues considered in clinical practice related to available dosage strengths. The investigator should contact the subject/guardian once the Week 32 lab results are available in order to provide guidance on the amount of the first glucocorticoid dose adjustment (if needed) during the open-label treatment period.

Table 11: Guide for Glucocorticoid Dose Adjustment During the Open-Label Treatment Period

Percent Change from Week 28 in Serum Androstenedione	Androstenedione Level	Glucocorticoid Dose Adjustment
Any increase	>ULN	Consider whether glucocorticoid dose needs to be increased
Any increase	≤ULN	Maintain current glucocorticoid dose
No change a	Any	Maintain current glucocorticoid dose
Decrease of ≤20%	Any	1 to 2 mg/m²/day glucocorticoid dose reduction
Decrease of >20% to ≤40%	Any	2 to 3 mg/m²/day glucocorticoid dose reduction
Decrease of >40%	Any	3 to 4 mg/m²/day glucocorticoid dose reduction

ULN=upper limit of normal

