## 9.8.2. Randomized, Double-Blind, Placebo-Controlled Treatment Period (Day 1 up to Week 28)

## **9.8.2.1.** Baseline (Day 1)

Baseline/Day 1 is defined as the first day of study drug dosing and should be the same as the day of randomization in the IRT.

Subjects should take their evening glucocorticoid dose prior to 2100 hours the night before the visit and should hold their morning dose of glucocorticoid and fludrocortisone (if applicable) on the day of the visit until after the predose blood sample collection, with dosing to occur between approximately 0800 and 0830 hours.

Subjects should be fasting, with no food from midnight the previous night until after the predose blood sample collection, after which they can have breakfast; subjects <6 years of age for whom the investigator deems that fasting until 0800 hours is not feasible can have a snack(s) if needed but should wait to have breakfast until after blood sample collection.

- Update inclusion/exclusion criteria as needed; subjects who continue to be eligible for the study will be randomized.
- Update medical history as needed.
- Perform a physical examination, including Tanner stage. Tanner stage will not be required to be assessed at Day 1 if the investigator determines that the Tanner stage is unlikely to have changed since screening; in this case, the screening Tanner stage will be considered the baseline.
- Perform vital signs, height, and weight.
- Collect blood samples for chemistry, TSH, free T4, hematology, and coagulation labs; fasting lipids and HOMA-IR; cortisol, LH, FSH, testosterone, PRA.

- Collect blood samples for 17-OHP, A4, and ACTH.
  - For subjects who are ≥6 years of age with a body weight ≥20 kg: approximately 15 minutes before and just prior to dosing with the morning glucocorticoid and at 2, 3, 4, and 6 hours after dosing. Any midday glucocorticoid dose that the subject is receiving should be taken after the 6-hour postdose blood sample collection. For subjects with body weight ≥20 to <30 kg, only a single sample for ACTH will be collected, which will be the sample just prior to the morning glucocorticoid dose.

  - For subjects who are <6 years of age or with a body weight <20 kg: blood sample collected prior to dosing with the morning glucocorticoid.

- Collect urine sample for urinalysis and (only for subjects of childbearing potential) urine pregnancy test.

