# 10.3. Glucocorticoid Total Daily Dose

Descriptive statistics will be presented by treatment group and visit for the glucocorticoid total daily dose (mg/m^2/day) observed, change from OL baseline, and percent change from OL baseline values to Week 52. Mean ( $\pm$ SEM) values of the glucocorticoid total daily dose (mg/m^2/day) at each visit will be summarized in line graphs by treatment group. Similar graphs will be presented for the change from OL baseline and percent change from OL baseline. These summaries will be presented for both the glucocorticoid total daily doses *without* the derivation of 0 for loss of androstenedione control as well as the glucocorticoid total daily doses *with* the derivation of 0 for loss of androstenedione control (only for subjects with a decrease in glucocorticoid total daily dose).

The above summaries will be repeated for the change from baseline to Week 52 in glucocorticoid total daily dose.

Similar to the responder analysis defined in Section 9.5.1, a physiologic glucocorticoid dose responder will be defined as the achievement of a reduction in glucocorticoid total daily dose to physiologic levels ( $\leq 11 \text{ mg/m}^2$ /day hydrocortisone equivalent adjusted for BSA) at OL period visits through Week 52, while androstenedione is adequately controlled at  $\leq 120\%$  of baseline or  $\leq$ ULN for age and sex, respectively, at each given visit. Androstenedione control will be assessed based on the androstenedione values at study baseline and each respective OL period visit through Week 52 following the same method as described in Section 6.3.3. Descriptive statistics will be presented by treatment group for the number and percentage of subjects classified as responders and non-responders at each visit in the OL period.

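### In the open-label period, the Week 32 adjustment table and the 'At all visits' sentence can point in opposite glucocorticoid dose directions for the same A4 result, and no precedence is stated

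*Protocol*

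**What the plan says.** For children on more than 11 mg/m²/day at Week 32, Protocol Section 7.3 bases the first open-label glucocorticoid step on Table 5, whose reference column is headed "Percent Change from Week 28 in Serum Androstenedione". The table has three rows for a decrease, and each gives 'Any' as the A4 level:

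- fall of up to 20%: "1 to 2 mg/m²/day glucocorticoid dose reduction"
- fall above 20% and up to 40%: "2 to 3 mg/m²/day glucocorticoid dose reduction"
- fall above 40%: "3 to 4 mg/m²/day glucocorticoid dose reduction"

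Table 11 in Section 9.3.2.2 and the Synopsis table repeat these rows. A footnote lets the investigator treat a change within ordinary variability as 'No change', for which the dose is maintained.

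After Table 6, after Table 12 and in the Synopsis, the protocol adds: "At all visits, if A4 is >120% of baseline and >ULN, increase glucocorticoid dose as appropriate in order to maintain A4 control".

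Two places settle what baseline means. Protocol Section 9.8.2.1 says "Baseline/Day 1 is defined as the first day of study drug dosing". SAP Section 10.3 says, for the open-label period, "Androstenedione control will be assessed based on the androstenedione values at study baseline and each respective OL period visit through Week 52". The SAP gives Week 28 its own name, OL baseline (Section 6.3.2).

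**The concern.** The table and the sentence use different reference points. The decrease rows ask only whether A4 is lower than at Week 28. The sentence asks whether A4 is still more than 20% above Day 1 and above the ULN. A child whose A4 had risen well above Day 1 by Week 28 can meet both conditions at Week 32, and the two instructions then point in opposite directions. The rows for an increase take the ULN into account; the rows for a decrease do not.

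Such children are foreseeable. SAP Section 9.4.2 has a rule for those who reduced their dose and lost A4 control by Week 28. Glucocorticoid is to be held stable from Week 28 to Week 32 as far as possible, and the schedule of assessments marks no potential adjustment at Week 28. Week 32 is thus the first scheduled open-label decision. Sites stay blinded to the randomized group, so they cannot use it to settle the question.

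At stake are whether sites handle the same result alike, the safety of the child concerned, and the Week 52 summaries of glucocorticoid dose and A4 control.

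**Working it through.** There is no planned figure to reproduce. The check is whether the two conditions can hold together.

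**Inputs.** R = Week 28 A4 / Day 1 A4. d = fractional fall from Week 28 to Week 32. The row limits (20%, 40%) come from Tables 5 and 11, the 120% and ULN conditions from the sentence, and the ULN values from SAP Table 3. One A4 value per visit is assumed to serve both instructions.

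**Conditions.** The table suggests a reduction when d > 0. The sentence calls for an increase when R(1 − d) > 1.2 and A4 > ULN. Both apply when

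d < 1 − 1.2/R, with A4 > ULN.

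| R | Both apply for falls below |
|---|---|
| 1.3 | 1 − 1.2/1.3 = 7.7% |
| 1.5 | 1 − 1.2/1.5 = 20% |
| 1.8 | 1 − 1.2/1.8 = 33.3% |
| 2.0 | 1 − 1.2/2.0 = 40% |
| 2.5 | 1 − 1.2/2.5 = 52% |
| 3.0 | 1 − 1.2/3.0 = 60% |

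Small falls classed as 'No change' drop out of these ranges.

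**Main example (assumed values).** Day 1 = 500, Week 28 = 900, Week 32 = 700 ng/dL.

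- Fall from Week 28: 1 − 700/900 = 22.2%, so the row is a 2 to 3 mg/m²/day reduction.
- Relative to Day 1: 700/500 = 140%, above 120%.
- 700 exceeds the highest A4 ULN in SAP Table 3, which is 265 ng/dL, so the sentence calls for an increase.

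**One example for each row (assumed values, ng/dL).**

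| Child | ULN | Day 1 | Week 28 | Week 32 | Fall | Table row | % of Day 1 | Sentence |
|---|---|---|---|---|---|---|---|---|
| Male, Tanner II-III | 82 | 100 | 200 | 165 | 17.5% | reduce 1 to 2 | 165% | increase |
| Female, Tanner IV-V | 220 | 300 | 600 | 400 | 33.3% | reduce 2 to 3 | 133% | increase |
| Male, Tanner II-III | 82 | 100 | 300 | 150 | 50% | reduce 3 to 4 | 150% | increase |

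**Comparison with Week 4.** In Tables 3 and 9 the fall is measured from Day 1. Any fall puts A4 below 100% of Day 1, so it cannot also be above 120%. The overlap exists only because the open-label table refers to Week 28.

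**The case against.** The best defence is that neither text is absolute. The table is offered as a suggestion, the first step is taken only if needed, and the sentence leaves the increase to be made as appropriate. Section 7.3 sets the dose target on condition that A4 is controlled. Section 7.2 defines control as the exact complement of the trigger in the sentence. An instruction for all visits, placed beside a suggested table, reads naturally as the override. Much of this stands: two sites could act differently, but it is not shown that they would. It does not remove the conflict. The flexibility stated for the table concerns the amount and the available dosage strengths, not the direction, and the decrease rows expressly cover any A4 level.

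The overlap may also be narrow. Section 5.3 cites a median A4 reduction of about 60% after 14 days at 100 mg bid in adults, the exposure that the paediatric doses are meant to match. A fall of that size needs R > 1.2/0.4 = 3.0 for both instructions to apply. This suggests that the overlap lies with weaker responders or large losses of control, though adult data cannot settle it. A dose changed at about Week 34 is also retested at Week 36, and later steps are scheduled.

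A reader might infer more than the documents support:

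- **That those affected are mainly placebo children.** No frequency is given for either group. The 150% and 180% thresholds in SAP Section 9.4.2.2 are alternative definitions of control at Week 28 and do not count children at Week 32.
- **That the table was carried over from Table 3 by oversight.** Section 7.3 gives a reason for the Week 28 reference: it gauges A4 after four weeks on open-label drug with stable glucocorticoid. For the same reason, its difference from the Day 1 reference in SAP Section 10.3 is not a separate error.
- **That Week 52 predicted adult height is affected.** Nothing in the documents shows such an effect.

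**Conclusion.** The inconsistency is real and should be corrected. For children on more than 11 mg/m²/day at Week 32, the two instructions conflict whenever R(1 − d) > 1.2 and A4 is above the ULN, unless the fall is classed as 'No change'. The documents do not say which prevails. This rests on baseline meaning Day 1, as both documents define it; if it meant Week 28, the conflict would vanish.

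The reach is limited. The primary and key secondary endpoints are at Weeks 4 and 28 and are untouched. The open-label glucocorticoid and A4-control results are exploratory (SAP Section 4.5) and summarized descriptively (SAP Section 10.3). The number of children affected cannot be calculated from the documents. What makes the point worth raising is that one laboratory result can lead to opposite dose directions within a single subsection of the protocol. It carries no view on which instruction is clinically right.

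**What to change.** Reconcile Table 5, Table 11 and the Synopsis table with the sentence on all visits, and state in each of the three places which instruction takes precedence when both apply. The sponsor's clinicians decide the clinical content. The cost is a wording change by amendment or site memo, with no added visits, samples or subjects and no change to the planned analyses.
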